hypothetical monetary rewards (Johnson & Bickel, 2002). Appropriately modified versions of this battery will be completed again at the second prenatal care visit and 28-weeks gestation, and then 2-, 4-, 8-, 12-, 24-, and 48-weeks postpartum. We will also assess breastfeeding, including initiation, duration, and different levels of breastfeeding (e.g., exclusive, predominate, any). All women will complete the Postpartum Bonding Questionnaire to examine associations between breastfeeding and maternal/infant bonding (Brockington et al., 2001). Breastfeeding is associated with significant improvements in a wide range of maternal and infant health outcomes, but there have been few opportunities to examine experimentally altered rates of breastfeeding due to the absence of ethical methods to manipulate them (Ip et al., 2007). The proposed study may provide an opportunity to do so by altering smoking status, which in turn impacts breastfeeding duration (Higgins et al., 2010b). These assessments will be conducted with all subjects independent of smoking status or treatment condition. Women will receive \$50 per assessment independent of smoking status. We also plan to assess health outcomes and health care utilization for use in the cost-effectiveness analysis. Permission will be requested of all women to review maternal and infant health care records through one-year postpartum and to telephone mothers monthly during postpartum to review infant health and health care visits. Project staff will review records by obtaining faxed copies or visiting the offices of local providers/pharmacies at the time of each of the regularly scheduled assessments. We will track the incidence of smoking-related pregnancy complications, delivery complications, and maternal and infant health outcomes during the 1st year postpartum (all illnesses requiring a visit to a healthcare professional). Infant outcomes will include birth outcomes (mean birth weight, % low birth weight deliveries (< 2500 g), mean gestational length, % premature deliveries (< 37 weeks), incidence of NICU admissions and mean length of stay, and health outcomes through one year postpartum (respiratory distress syndrome, upper and lower respiratory infections, otitis media, sudden infant death syndrome, and other infant death). We will track all maternal prenatal and postpartum health care utilization including pharmacy use through one-year postpartum and infant utilization through one-

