## Statistical Methods

Study conditions will be compared on baseline demographics and other characteristics using analysis of variance for continuous variables and chi-square tests for categorical variables. If a specific characteristic differs significantly across study conditions and is predictive of outcome, it will be considered as a potential covariate in subsequent analyses. Analyses of treatment effects on smoking status will be limited to smokers randomized to the two treatment conditions. We will adhere to an intent-to-treat approach (Armitage, 1983) wherein all women randomized to the study conditions will be included in the analyses independent of early dropout, noncompliance, etc., with the exception of excluding women for abortion/fetal demise as is convention in this research area. Cochran Mantel Haenszel tests (CMH) will be performed for comparisons of the two treatment conditions on point-prevalence smoking abstinence at end-of-pregnancy and 6-months postpartum assessments with

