referring clinic as a stratification variable. The Breslow-Day Test will be used to examine the homogeneity of treatment effects across referring clinics. Comparisons of point-prevalence abstinence rates between treatment conditions across all assessments through one-year postpartum will be analyzed using mixed model repeated measures for categorical data based on generalized estimating equations (GEE) utilizing a logistic link function (SAS: PROC GENMOD, SAS Institute, Cary, NC). We will include women from the nonsmoker condition in analyses of fetal growth, birth outcomes, and breastfeeding and other postpartum outcomes. Comparisons of treatment conditions on dichotomous outcomes (e.g. % low birth weight, % preterm, % NICU admissions, % breastfeeding, % medical treatment in first year) will parallel categorical analyses for point prevalence abstinence using PROC GENMOD to adjust for strata (referring clinics) and potential covariate effects. Analysis of covariance will be used to compare study conditions on mean birth weight adjusting for variables known to predict birth weight (i.e., maternal prepregnancy BMI, parity, and sex), mean gestational age at delivery, and frequency measures of medical illnesses. Statistical analyses of fetal growth outcomes (i.e. estimated fetal weight, fetal lean area, fat area, femur length and head circumference) will be based on linear growth models with slope and intercept as random effects (SAS PROC MIXED). This methodology allows for the within-subjects ultrasound assessments not to be at identical timepoints across subjects. Study condition will be considered a fixed factor with fetus nested within study condition. Two-way analyses of covariance will also be used for analyzing effects of study condition and referring clinic on DEXA body composition measures at 12 months. Additional subject level covariates will include maternal pre-pregnancy body mass index, maternal age and fetal gender. Analyses of infant growth will parallel those used to examine fetal growth. Repeated measures analyses of variance will be used to test for differences between study conditions in skinfold thickness obtained during infant 1st year of life and continuous measures of medical illnesses. Significance will be based on alpha = .05 for all analyses.

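### Illness frequencies go to ANCOVA without being defined as count or rate and with no allowance for time observed, so unequal observation would bias the comparison

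*Combined protocol and SAP*

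**What the plan says.** In Statistical Methods, the sentence that opens "Analysis of covariance will be used to compare study conditions on mean birth weight" goes on, after the birth-weight covariates, to "mean gestational age at delivery, and frequency measures of medical illnesses". It reads most naturally as three outcomes handled by one method. A later sentence gives repeated measures ANOVA to "continuous measures of medical illnesses" without saying how these differ from the frequency measures.

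The same section sets the intent-to-treat rule: "all women randomized to the study conditions will be included in the analyses independent of early dropout, noncompliance, etc". The only exception is abortion or fetal demise. The rule speaks of randomised women. The never-smokers, who are not randomised but enter the postpartum comparisons, have no stated rule.

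The Assessments section says what is collected: "maternal and infant health outcomes during the 1st year postpartum (all illnesses requiring a visit to a healthcare professional". It names two sources. The first is records: "Permission will be requested of all women to review maternal and infant health care records through one-year postpartum", obtained as faxed copies or by "visiting the offices of local providers/pharmacies at the time of each of the regularly scheduled assessments". The second is a plan "to telephone mothers monthly during postpartum to review infant health and health care visits".

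No section defines the frequency measure as a count or a rate, gives an observation-time denominator or offset, or says what to do with a mother or infant whose follow-up is incomplete.

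**The concern.** A count of illnesses grows with the time over which illnesses can be found. ANCOVA on a count has no place for that time, so a count from part of a year is read like a count from a full year. If one condition is observed for longer on average, it will seem to have more illness. Should that be the condition with the real health benefit, the benefit is partly hidden.

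Observation could differ between conditions. Monthly calls need continued contact. Record review is directed at local providers, so a family that changes provider or moves can be lost. Permission can be withdrawn, and an infant death ends observation. Under Treatment Conditions, the incentives arm has paid monitoring visits to 12 weeks postpartum, while never-smokers have no contact beyond assessments, ultrasounds and calls.

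The plan allows for unequal time elsewhere. The Economic Evaluation adds a cost per person per week because treatment duration varies, and the fetal growth model is justified partly because scans need not fall at the same times. Illness frequency has no equivalent.

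**Working it through.** **1. Inputs from the documents.** 115 per condition and two-sided 0.05 (Sample Size Justification); alpha 0.05 for all analyses (Statistical Methods). The documents give no illness rate, SD, power, dropout rate or observation time for illness frequency, so there is no plan figure to reproduce. Everything below is illustrative.

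**2. Assumptions.** A proportion d of a condition is lost, at a time uniform over the year (half a year observed on average). A share r of those lost still have complete records. The illness rate is the same in both conditions and unrelated to loss.

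**3. Formula.** Expected count = rate × mean observed time. Mean observed time = 1 − d(1 − r)/2. With no true difference, the ratio of mean counts is therefore the ratio of mean observed times. With a true rate ratio, the two multiply.

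**4. Results.** Rejection rates come from 3,000 simulated trials per setting: 115 per condition, no true difference, mean 4 illnesses per year, gamma frailty with shape 1. The test of means has no covariates. The person-time test compares events divided by time, with a robust variance.

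| Loss, A vs B | r | Mean time A / B | Ratio of mean counts | Type I error, means | Type I error, person-time |
|---|---|---|---|---|---|
| 20% vs 20% | 0 | 0.90 / 0.90 | 1.00 | 4.8% | 5.9% |
| 10% vs 20% | 0 | 0.95 / 0.90 | 1.056 | 6.9% | 5.7% |
| 10% vs 30% | 0 | 0.95 / 0.85 | 1.118 | 11.0% | 5.1% |
| 20% vs 40% | 0 | 0.90 / 0.80 | 1.125 | 10.9% | 6.3% |
| 10% vs 20% | 0.8 | 0.99 / 0.98 | 1.010 | 4.2% | 4.6% |
| 10% vs 30% | 0.8 | 0.99 / 0.97 | 1.021 | 6.0% | 6.3% |
| 20% vs 40% | 0.8 | 0.98 / 0.96 | 1.021 | 6.0% | 6.1% |
| 10% vs 30% | 1 | 1.00 / 1.00 | 1.00 | 4.5% | 5.1% |

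In all these settings the person-time rate ratio averaged 0.995 to 1.005. The simulation error on a 5% rate is about √(0.05 × 0.95/3000) = 0.4 percentage points.

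**5. Hand check of the 10% vs 30% row, r = 0.** Difference in means: 4 × (0.95 − 0.85) = 0.40. Variance of a count: 4E(T) + 16[2E(T²) − E(T)²]. For 10% loss, E(T²) = 0.90 + 0.10/3 = 0.933 and the variance is about 19.2. For 30% loss, E(T²) = 0.70 + 0.30/3 = 0.80 and the variance is about 17.4. SE = √((19.2 + 17.4)/115) = 0.564, so the shift is 0.40/0.564 = 0.71. Rejection is P(Z > 1.25) + P(Z < −2.67) ≈ 0.106 + 0.004 = 0.11, as simulated.

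**6. Later loss.** If loss falls uniformly between weeks 12 and 52, a leaver is observed for 32/52 = 0.615 of the year. At 10% vs 30% loss, mean times are 1 − 0.10 × 0.385 = 0.962 and 1 − 0.30 × 0.385 = 0.885, a ratio of 1.09.

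**7. Is skew itself the problem?** A second simulation (700 trials per setting, 110 per arm, negative binomial counts, mean 5 per year, dispersion 0.5 taken as known) had no loss. The test of means had size 4.1% and power 66.3% for a 25% reduction; the negative binomial model had 4.4% and 68.0%. With the later loss of step 6 and no records after it, size was 12.1% vs 6.1% and power 38.3% vs 67.7%. Observation time does the damage; the shape of the distribution does little.

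**The case against.** Two stronger readings are tempting. One is that the plan compares raw counts. The text does not say so: a frequency measure could be a count, a count per period or a rate. The other is that a woman who drops out is scored as having few illnesses. The intent-to-treat rule keeps her in the analysis but does not say that unobserved months count as illness-free.

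Nor does stopping attendance end observation. All women are asked for record access through one year, and the Assessments section reports 100% permission over 10 years of earlier trials. The cost-benefit analysis draws on claims data for mother and infant to 12 months. Eligibility requires a plan to stay in the area through 12 months postpartum. Assessments, assessment payments, record review and calls are the same for all conditions, and the extra incentives-arm contact ends at 12 weeks postpartum. Differential loss afterwards is possible but not shown.

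Most of this stands, and it makes the bias conditional and probably small. It does not close the gap. Permission is not complete capture. The earlier record system served birth outcomes and is only now being extended to a year, and no one-year completeness figure is given. The claims data are described for costs, not for the illness comparison. The missing definition and denominator remain.

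**Conclusion.** The point holds in conditional form. The plan names a method for illness frequency that takes no account of observed time, and it leaves the measure undefined. If counts are used and observed time differs between conditions, the better-observed condition shows a false excess equal to the ratio of mean observed times. That is about 6% to 13% when losses differ by 10 to 20 points and nothing is recorded afterwards, about 1% to 2% if records are complete for 80% of leavers, and nothing if observation is equal or complete. Under equal but incomplete observation the ratio is unbiased, though a true mean difference shrinks in proportion to the time observed.

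These sizes rest on assumed loss and illness rates. The documents do not show that observation will differ, or in which direction. A reader might also infer that ANCOVA is unsafe here because counts are skewed; at about 110 per arm the check gives that little support. Illness frequency is not among the primary hypotheses listed in the Sample Size Justification, so the point is minor to moderate.

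**What to change.** - Define illness frequency as events per person-time, for mother and infant separately, and say how it differs from the illness measures given to repeated measures ANOVA.
- Replace ANCOVA for these outcomes with negative binomial regression in PROC GENMOD, with log observed time as offset, referring clinic and the covariates the plan already provides for. Report rate ratios with 95% confidence intervals.
- Define observed time from documented record or call coverage, not attendance, and apply the same rule to never-smokers.
- Report observed time by condition, and add a sensitivity analysis for incomplete records.

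The cost is SAP wording and recorded coverage dates for each mother and infant; the software is unchanged. Effects become rate ratios instead of mean differences. The offset assumes that loss is unrelated to illness and that the rate is roughly constant over the year. It does not cure informative loss, which is why the sensitivity analysis is needed. With complete follow-up almost nothing is given up.

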### **Monitoring Fetal/Infant Health**

**Fetal Growth.** We will compare the growth profiles for each of the fetal parameters measured across study conditions. This includes abdominal circumference, head circumference, femur length, estimated fetal weight and mid-thigh lean body and fat areas. We will also characterize birth weight between conditions employing birth weight percentiles (Bernstein et al., 1994; 1996; Fry, 2002). We have developed ultrasound techniques that are capable of distinguishing and quantifying specific fetal body

compartments with focus on the lean body and fat mass compartments (Bernstein et al., 1991; 1997; 2000). We will use this ultrasound technology to examine participants at 30 and 34 weeks of pregnancy to estimate changes in overall fetal growth and body composition. We will estimate fetal weight according to the method of Hadlock et al (1985) employing head circumference, femur length and abdominal circumference. We will estimate fetal peripheral muscle and fat areas according to the methods we have developed (Bernstein et al., 1991; 1997; 2000) and are now used broadly (Galan, 2001; Padoan, 2004; Larciprete et al., 2003). **Infant Growth.** Infant growth measures will also be obtained at 6 and 12 months. Weight will be obtained through the use of an electronic scale and length measurements will employ a measuring board that employs the tonic neck reflex for accurate assessment of infant length, thereby estimating ponderal index (Rohrer 1921, Walther & Ramaekers, 1982). At 6 and 12 months we will also measure skinfold thickness at 5 sites (triceps, subscapular, flank, anterior thigh and abdominal wall) (Bernstein 1991, 1997) to estimate subcutaneous fat stores. At 12 months only we will conduct an assessment of infant body composition using whole body dual x-ray absorptiometry (DEXA).

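### The 12-month DEXA and the 6- and 12-month skinfolds are analysed at nominal ages, without the infant's actual age at measurement

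*Combined protocol and SAP*

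**What the plan says.** The Infant Growth paragraph of Monitoring Fetal/Infant Health sets the timing: "Infant growth measures will also be obtained at 6 and 12 months", and "At 6 and 12 months we will also measure skinfold thickness at 5 sites". DEXA is done at 12 months only. No allowable range around these ages is given there or elsewhere.

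Statistical Methods then gives each outcome its model.

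- **Fetal growth:** a linear growth model with random slope and intercept, chosen with timing in mind: "This methodology allows for the within-subjects ultrasound assessments not to be at identical timepoints across subjects".
- **Infant growth:** "Analyses of infant growth will parallel those used to examine fetal growth". This can be read to cover infant weight and length.
- **DEXA:** "Two-way analyses of covariance will also be used for analyzing effects of study condition and referring clinic on DEXA body composition measures at 12 months". The next sentence completes the model: "Additional subject level covariates will include maternal pre-pregnancy body mass index, maternal age and fetal gender".
- **Skinfolds:** "Repeated measures analyses of variance will be used to test for differences between study conditions in skinfold thickness obtained during infant 1st year of life". No covariates are named.

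DEXA and skinfolds therefore have their own models, and infant age at measurement is in neither.

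**The concern.** Body composition and subcutaneous fat can change with age during the first year. A model that knows only the label 12 months treats an infant seen somewhat early and one seen somewhat late as the same age. If the scatter in age is alike in all conditions, it only adds residual variance. If one condition is on average measured later, the difference in age enters the comparison as a difference in body composition. Randomisation does not exclude this, because visit timing arises after randomisation, and the never-smoker condition is not randomised at all.

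The plan saw this problem for fetal scans and solved it there. The same reasoning was not carried to these two outcomes. They are not among the primary hypotheses listed under Sample Size Justification, so what is at stake is the precision and interpretation of supporting results.

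**Working it through.** **No figure of the plan to reproduce.** The documents state no SD, expected difference or power for DEXA or skinfolds. For scale only, the nearest stated figure is birth weight (Sample Size Justification): 200 g, SD 550 g, 115 per condition, 80% power. Recomputed power is 78.7%, in line with the plan; the target is 200/550 = 0.36 SD.

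**Inputs from the documents.** 115 per condition; two-sided alpha 0.05.

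**Assumed inputs.** Change in the outcome of 0.02 to 0.08 SD per week of age, where the SD is that at a fixed age; SD of age at measurement 2 to 4 weeks; difference in mean age between two conditions of 0, 1 or 2 weeks.

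**Step 1: timing alike across conditions.** Bias is 0. The residual SD is multiplied by sqrt(1 + (rate x SD of age)^2).

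- Low end: sqrt(1 + (0.02 x 2)^2) = 1.0008, an increase of 0.1%.
- High end: sqrt(1 + (0.08 x 4)^2) = 1.050, an increase of 5.0%.

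**Step 2: timing differs.** Bias b = gap x rate. With no true effect, the chance of a significant result is Phi(b/se - 1.96) + Phi(-b/se - 1.96), with se = sqrt(2/115) = 0.132 SD.

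| Gap in mean age | Bias at 0.02 / 0.05 / 0.08 SD per week | False-positive rate |
|---|---|---|
| 0 weeks | 0 / 0 / 0 SD | 5.0% |
| 1 week | 0.02 / 0.05 / 0.08 SD | 5.3% / 6.7% / 9.3% |
| 2 weeks | 0.04 / 0.10 / 0.16 SD | 6.1% / 11.8% / 22.8% |

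Example, last cell: b/se = 0.16/0.132 = 1.21, and Phi(1.21 - 1.96) is about 0.23. The table takes all 115 infants per condition as measured. With an assumed 80, the 2-week row becomes 5.7% / 9.7% / 17.3%.

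**Step 3: scale.** The smallest difference detectable with 80% power is (1.96 + 0.84) x sqrt(2/115) = 0.37 SD. A bias of 0.02 to 0.16 SD is 5% to 43% of that.

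**Step 4: does adding age cure it?** Simulation with 4,000 runs, an assumed 80 infants per condition, 0.05 SD per week, SD of age 3 weeks, a 2-week gap and no true effect:

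- Without age: mean bias 0.10 SD, false-positive rate 9.5%.
- With age: mean bias 0.00 SD, false-positive rate 5.3%.

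With no gap, the two models reject at 5.4% and 5.1%, so including age does no harm.

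**The case against.** The best reply is that nothing in the documents shows timing will differ, and without a difference there is no bias. That stands. The Assessments section gives every participant the same schedule and the same payment, regardless of condition. A reader might infer a lag from the postpartum voucher visits of the incentives condition: 360/45 = 8 visits at 45 dollars each, which the other conditions do not have. But those visits end at 12 weeks postpartum, long before the 6- and 12-month measures.

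A reader might also infer that 6 and 12 months fall outside the assessment schedule, because the listed assessments are at 24 and 48 weeks, about 2 and 4 weeks earlier. From there a 4-week gap between conditions, with a bias of 0.08 to 0.32 SD, is easily imagined. The documents do not support this. Statistical Methods tests abstinence at 6 months where Sample Size Justification powers it at 24 weeks, so the labels are used interchangeably. Never-smokers have listed assessments at 24 and 48 weeks and no further contact beyond the scans and calls described, which suggests their infants would be measured at those assessments. A 4-week gap would need one condition measured at 48 weeks and another at the calendar year.

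The sentence on infant growth paralleling fetal growth is a fair reply for weight and length, and these are not part of the point. It does not reach DEXA and skinfolds, which are given different models. The covariate rule that opens Statistical Methods does not fill the gap either: it follows the baseline comparisons, depends on a significant difference, and commits only to considering a variable. The DEXA covariate list need not be exhaustive, but a plan should name a variable this basic.

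**Conclusion.** The point holds as a modest improvement to two stated models outside the primary hypotheses. Infant age at measurement is missing from both the DEXA and the skinfold analysis, while the plan accommodates unequal timing for fetal scans.

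The certain part is small: some loss of precision, 0.1% to 5% in SD under the assumed growth rates and age scatter. The bias is conditional: 0.02 to 0.16 SD if mean age differs by 1 to 2 weeks, and zero if it does not. Both figures depend on the assumed 0.02 to 0.08 SD per week. The documents supply no rate for either outcome, and a skinfold that hardly changes with age over the weeks in question would fall at or below the low end. It would be wrong to conclude that the condition comparison is biased. The case for acting is that the remedy is nearly free and makes the question moot.

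**What to change.** In Statistical Methods, add exact infant age at measurement (date of measurement minus date of birth) as a covariate in the DEXA analysis of covariance. Replace the repeated measures analysis of variance for skinfolds with a mixed model that uses actual age. State that the measurement date is recorded for every infant; the documents do not say so.

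In Monitoring Fetal/Infant Health, add one sentence on how the 6- and 12-month measures relate to the 24- and 48-week assessments, the same for all conditions. A fixed window is not needed. One such as 52 weeks plus or minus 2 (50 to 54 weeks) would exclude a measurement made at the 48-week assessment and could force an extra visit, including for never-smokers.

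The cost is a few sentences, about one parameter per model, and a date that must be captured if it is not already.

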## Sample Size Justification

Sample size was determined to have sufficient power to detect differences between study conditions corresponding to our primary hypotheses regarding point prevalence smoking abstinence at late pregnancy and 24weekpostpartum assessments, fetal growth, birth weight, and breastfeeding. Estimates of abstinence were based on our prior trials where 7-day point-prevalence abstinence in the incentives vs. control conditions were 34% vs. 7% at the late-pregnancy assessment and 14% vs. 1% at 24weeks postpartum assessment, respectively (Higgins et al., 2010a). We estimated that the proposed increase in the value of the incentives used with heavier smokers will increase late-pregnancy abstinence rate to approximately 50% in the incentives condition while the best practices alone condition is estimated at <10%. Assuming a decline in abstinence of approximately 20% from late-pregnancy to the 24-week postpartum assessment as we saw in our prior trials, we estimate abstinence rates of approximately 30% vs. < 5% at 24weeks postpartum in the best practices plus incentives vs. best practices alone conditions, respectively. The proposed sample size of 115 per study condition will result in greater than 90% power to detect a difference between the two treatment conditions in abstinence rates of 50% vs. 10% at late-pregnancy or 30% vs. 5% at 24weeks postpartum assessments using a chi-square test. The proposed sample size is also expected to be more than sufficient for examining differences between study conditions in fetal growth, birth weight, and breastfeeding outcomes. The proposed sample size after considering noncompliance in completing scheduled ultrasounds is estimated to have power of 80% for detecting a mean growth difference of 23 g/wk in estimated fetal weight between any two conditions based on our estimated pooled within group SD=49.7. This difference is slightly more than half the difference observed between the incentive and control condition in our 2008 study (Heil et al, 2008) and represents a conservative expected difference. With respect to mean birth weight, power is estimated to be 80% to detect a difference of approximately 200 g between any two study conditions assuming a pooled SD=550, which aligns well with treatment effects in our study combining results across prior trials (Higgins et al., 2010a) where

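### Infant skinfolds at 6 and 12 months are assigned to repeated measures ANOVA with no fitting procedure or missed-visit rule; a likelihood mixed model would keep infants seen only once

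*Combined protocol and SAP*

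**What the plan says.** All references are to the combined protocol and SAP.

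- Monitoring Fetal/Infant Health, under Infant Growth, sets the schedule: "At 6 and 12 months we will also measure skinfold thickness at 5 sites".
- Statistical Methods gives fetal growth outcomes random-slope, random-intercept growth models in PROC MIXED. The stated reason is timing: "This methodology allows for the within-subjects ultrasound assessments not to be at identical timepoints across subjects".
- It then says "Analyses of infant growth will parallel those used to examine fetal growth".
- The sentence after the one on infant growth names a different method for skinfolds: "Repeated measures analyses of variance will be used to test for differences between study conditions in skinfold thickness".

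For that last analysis the plan gives no SAS procedure, covariance structure or rule for an infant measured at only one of the two visits. It states no missing-data assumption for continuous outcomes. In the Sample Size Justification, the only allowance for missed assessments concerns ultrasounds, and no rate is given.

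**The concern.** With two visits, the classical least-squares form of repeated measures ANOVA treats the pair of measurements as the unit. An infant seen only at 6 months or only at 12 months then contributes nothing. Two things follow.

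- **Precision.** Measurements that were taken are not used.
- **Validity.** Restricting to complete pairs is in general unbiased only if visits are missed completely at random. A likelihood-based mixed model using every observed visit needs the weaker missing-at-random assumption, under which missingness may depend on data already observed, such as the 6-month value.

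The plan already has the software and model family that avoid this, so the ANOVA label gives something up for no evident gain.

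**Working it through.** **The plan's own figure.** There is none to reproduce: no sample size, power, SD or missed-visit rate is stated for skinfolds. The only input taken from the documents is 115 per condition (Sample Size Justification). Everything marked as assumed below is not in the documents.

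**Assumed inputs**

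- m, the proportion of infants missing each visit: 10–25%, equal at both visits
- ρ, the correlation between an infant's two measurements: 0.4–0.8
- c, the correlation between missing one visit and missing the other: 0 at first, then varied

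**Step 1: who is observed (c = 0).** Both visits: (1−m)². Exactly one: 2m(1−m). Neither: m². At m = 0.15 these are 72.25%, 25.5% and 2.25%. So 27.75% of infants lack a complete pair, while 97.75% have at least one visit. The 2.25% with no visit are lost to either method.

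**Step 2: information on the visit-averaged condition effect.** In units of 1/σ², an infant with both visits contributes 2/(1+ρ), because the mean of two measurements has variance σ²(1+ρ)/2. An infant with one visit contributes 1. The standard error ratio, complete pairs over all observed visits, is therefore

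√{[(1−m)²·2/(1+ρ) + 2m(1−m)] / [(1−m)²·2/(1+ρ)]} = √{1 + m(1+ρ)/(1−m)}.

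With equal miss rates at the two visits, the ratio is the same if condition effects may differ by visit and are then averaged.

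| m | ρ = 0.4 | ρ = 0.8 |
|---|---|---|
| 0.10 | √1.1556, +7.50% | √1.2000, +9.54% |
| 0.15 | √1.2471, +11.67% | √1.3176, +14.79% |
| 0.25 | √1.4667, +21.11% | √1.6000, +26.49% |

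The extremes are 7.497% and 26.491% before rounding, hence about 7–26%. At 15% missed the range is 12–15%.

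**Step 3: correlated misses.** Families lost by 6 months tend to be missing at 12 months too, and no method recovers them. With correlation c, exactly one visit is seen in 2m(1−m)(1−c) of infants and both in (1−m)² + c·m(1−m). At m = 0.15 and c = 0.5 these are 12.75% and 78.625%.

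- ρ = 0.4: √(1 + 0.1275/(0.78625 × 2/1.4)) = √1.1135, or +5.5%
- ρ = 0.8: √(1 + 0.1275/(0.78625 × 2/1.8)) = √1.1460, or +7.0%

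So the inflation is about 6–7%. By the same formula at m = 0.15 it is 8–10% at c = 0.3 and 2–3% at c = 0.8.

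**Step 4: the same loss as numbers and power.** Take independent misses and an effect that would have 80% power (two-sided 0.05) if all 115 pairs per condition were complete. At 20% missed per visit, complete pairs number 115 × 0.64 = 73.6 per condition, against 115 × 0.96 = 110.4 with at least one visit. Complete-pair power is Φ(2.802 × 0.8 − 1.960) = 61%, where 2.802 = 1.960 + 0.842. With all observed visits it is 73–78% for ρ from 0.3 to 0.9. At 10% missed the figures are 71% against 77–79%.

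**Step 5: bias, as an illustration only.** Suppose that in one condition the 12-month visit is missed by 35% of infants with below-average 6-month skinfolds and 5% of the others (20% overall). The 6-month mean among complete pairs is then too high by 0.5 × 0.798 × (0.95 − 0.65)/0.80 = 0.15 SD, where 0.798 SD is the mean distance from the centre of a normal distribution. The two-visit mean is off by 0.15 × (1+ρ)/2, which is 0.11 SD at ρ = 0.5 and 0.13 SD at ρ = 0.7. Simulation gave the same figures, and a bias of about 0 for the likelihood estimate.

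**Step 6: nothing is lost when data are complete.** On one simulated complete data set, repeated measures ANOVA and a compound-symmetry mixed model gave the same between-condition F (0.2801 in each). After 20% of visits were deleted, the mixed fit kept 111 of 120 infants, of whom 69 had both visits.

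**The case against.** The strongest reply is that the plan nowhere says an infant with one visit will be removed. That stands. A reader might infer a planned deletion, but it follows only from the usual least-squares fit, and the same model fitted by likelihood keeps those infants. Skinfolds are described under Infant Growth, so the sentence "Analyses of infant growth will parallel those used to examine fetal growth" could even be read as covering them. The section also uses labels loosely, calling a GEE analysis a mixed model. Against this, skinfolds get a sentence of their own with a different method named, so the classical reading is plausible, though not certain.

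Three further inferences are tempting and are not supported.

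- **A breach of intent-to-treat.** The plan says "all women randomized to the study conditions will be included in the analyses independent of early dropout, noncompliance, etc". That sentence is about randomized women and does not say how a partly missing infant measurement is handled. The never-smokers, who may be part of these comparisons, were not randomized. A mixed model would also leave out infants with no visit, so it would not satisfy a literal reading either.
- **The same fault in the continuous illness measures named in that sentence.** Those data come from record review and monthly calls, so a missed skinfold visit does not remove them.
- **An internal contradiction over PROC MIXED.** The plan justifies it by unequal ultrasound timing, not by missing data. Choosing another method for skinfolds is less efficient but not inconsistent.

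It is also fair to say that independent misses are the assumption least favourable to the ANOVA among those tried. Moderate persistence of dropout roughly halves the loss. Nothing in the documents shows that completers would differ by condition.

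**Conclusion.** The point holds as a cheap improvement to an analysis that is not fully specified. It is not an error that undermines the trial. The method named for skinfolds, in its usual form, discards infants seen once and generally needs data missing completely at random; a method already in the plan does neither.

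The size is unknown because the documents give neither a missed-visit rate nor a within-infant correlation. The 7–26% inflation in standard error depends on the assumed ranges and on independent misses. At 15% missed it is 12–15% if misses are independent and about 6–7% if they correlate 0.5. The bias example shows a mechanism and is not a forecast.

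Impact is limited: skinfolds are not among the outcomes named in the primary hypotheses, and no power statement rests on them.

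**What to change.** In Statistical Methods, replace the repeated measures ANOVA for skinfold thickness with a likelihood-based linear mixed model in PROC MIXED. Include condition, visit and condition-by-visit, use an unstructured covariance for the two visits (three parameters), and use all observed visits. State that the analysis assumes visits are missing at random given the observed data.

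The cost is a change of SAP wording, with no new data and no new software. The small downside is reliance on the missing-at-random assumption, which cannot be verified from the data and should therefore be written down. It is weaker than the assumption that a complete-pair analysis generally needs.
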